Condensed and Distributed Robotic Therapy in Spastic Stroke Post Botulinum Toxin
Injection

NCT03321097

Document date Dec, 29, 2016

Spasticity, a common impairment after stroke, has a profound impact on activity and participation for patients. According to the result of our ongoing study, we found Botulinum Toxin A (BoNT-A) injection combined with robot-assisted training is recommended to enhance functional recovery for patients with spastic hemiplegic stroke. However, the optimal program as considering the Robotic Therapy (RT) frequency is unknown.

The aims of this study are to determine and compare the immediate and longer-term effects between condensed and distributed programs of RT following BoNT-A injection in subjects with spastic hemiplegic stroke.

Methods

Participants with stroke will be recruited from a rehabilitation department of tertiary referral hospital. Patients who have spastic hemiplegic stroke are screened for eligibility to join the study. The inclusion criteria will be: (1) clinical and imagine diagnosis of a first or recurrent unilateral stroke ≥ 3 months; (2) upper limb spasticity (modified Ashworth scale of $\geq 1+$ for elbow flexor and/or forearm pronator and/or finger flexor muscles and/or wrist flexor muscles (Bohannon & Smith, 1987); (3) initial motor part of UE of FMA score ranging from 12 to 56, indicating moderate to severe movement impairment (Duncan, Goldstein, Matchar, Divine, & Feussner, 1992; Fugl Meyer, Jaasko, & Leyman, 1975; Park, Wolf, Blanton, Winstein, & Nichols-Larsen, 2008); (4) no serious cognitive impairment (i.e., Mini Mental State Exam score > 20) (Teng & Chui, 1987); (5) age ≥ 18 years ; and (6) willing to provide written informed consent. Participants will be excluded if they are pregnant, or with bilateral hemispheric or cerebellar lesions, sever aphasia, significant visual field deficits or hemineglect, contraindication for BoNT-A injection, treatment with BoNT-A within 4 months before recruitment, any fixed joint contracture of the affected upper limb, or a history of orthopedic or other neurological diseases and/or medical conditions that would prevent adherence to the rehabilitation protocol.

Participants with will be recruited and randomly assigned to either condensed or distributed RT groups post BoNT-A injection. Each training session included 40 minutes RT, followed by 40-minute functional training. The condensed group will receive 4 sessions per week, for 6 weeks, the distributed group 2 sessions per week, for 12 weeks. Body function and structures outcome measures include Fugl-Meyer Assessment, Modified Ashworth Scale, actigraphy. Activity and participation measures include Wolf Motor Function Test, Motor Activity Log, and Canadian Occupational Performance Measure. In addition, to directly reflect a patient's unique needs and goals, Goal Attainment Scaling will be assessed. Evaluators will be blind to group allocation. The outcome will be measured at pre-treatment, mid-treatment,

post-treatment, and 6-week follow-up.

Data Analysis

To examine the baseline differences among 2 groups, we use the chi-square test and independent-sample t tests to compare participants' baseline characteristics between groups. To examine the therapeutic effects of the RT, we use mixed ANOVA to test the differences within groups across 4 measurement time points (time effect) and to test the differences between groups (condensed intervention group and distributed intervention group) and to test interaction effect between time and group. Pairwise comparison with Bonferroni adjustments is used to examine the differences between measurement time points. All tests are executed using the SPSS software version 25 (International Business Machines Corp., Armonk, NY) at the $\alpha = .05$ level of significance.

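### Time since stroke is unrestricted above 3 months but absent from the between-program model, which costs precision and leaves any chance imbalance uncorrected

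*Combined protocol and SAP*

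**What the plan says.** Methods, inclusion criterion (1), admits patients with "clinical and imagine diagnosis of a first or recurrent unilateral stroke ≥ 3 months". Neither the other inclusion criteria nor the exclusions cap time since stroke. The only time-based exclusion concerns earlier toxin: "treatment with BoNT-A within 4 months before recruitment".

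The paragraph on allocation says that participants are "randomly assigned to either condensed or distributed RT groups post BoNT-A injection". It names no stratification or minimisation factor.

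Under Data Analysis, "we use the chi-square test and independent-sample t tests to compare participants' baseline characteristics between groups". The characteristics are not listed, and the plan does not say what follows if one of them differs. The outcome model is a mixed ANOVA with time (four assessments), group and time-by-group. It has no covariate. No sample size, standard deviation or target difference is given anywhere.

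**The concern.** A patient 3 months after stroke may still improve without further treatment, while one several years out is expected to be stable. If so, time since stroke predicts change in outcomes such as the Fugl-Meyer score. Leaving a predictor of change out of the model has two consequences.

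- The variation it explains stays in the error term, so the between-program comparison is less precise than it could be, even when the arms are perfectly balanced.
- If chance puts more early patients in one arm, the estimate from that one trial shifts by their extra recovery, and nothing in the analysis removes the shift.

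The baseline tests are no safeguard. In a small trial they have little power to detect an imbalance that matters, and the plan attaches no action to them.

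**Working it through.** The plan has no figure on this point to reproduce. Everything below is illustration. **Assumed, not from the documents:** 15, 20 or 30 per arm; 20% to 50% of patients early after stroke; an extra gain of 2 to 8 Fugl-Meyer points in early patients by the assessment; residual SD of change 5. The illustration splits patients into early and late, although the covariate proposed under the fix is continuous.

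**1. Chance imbalance.** The number of early patients in each arm is binomial(n, f). The probability that the two proportions differ by at least 20 percentage points is:

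| Per arm | f = 20% | f = 30% | f = 50% |
|---|---|---|---|
| 15 | 0.25 | 0.32 | 0.36 |
| 20 | 0.16 | 0.23 | 0.27 |
| 30 | 0.08 | 0.12 | 0.15 |

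**2. Would the baseline test flag it?** Take 4/20 against 8/20 early. The uncorrected chi-square is 40 × (4×12 − 16×8)² / (20×20×12×28) = 256,000 / 134,400 = 1.90, so p = 0.17 (0.30 with continuity correction). It would not be flagged at 0.05.

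**3. Size of the shift.** Shift = imbalance × extra gain. With 5 points, 0.20 × 5 = 1.0 point. With 4 or 8 points it is 0.8 or 1.6.

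**4. Shift against the standard error.** Unadjusted variance of change = 5² + f(1−f) × gain². With f = 30% and a 5-point gain this is 25 + 0.21 × 25 = 30.25. At 20 per arm, SE = √(30.25 × 2/20) = 1.74. A shift of 1.0 is therefore 0.57 of a standard error. With the 4/20 against 8/20 split held fixed, a 5-point gain and no program effect, the simulated false-positive rate was about 0.07 instead of 0.05.

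**5. Precision.** Share of variance explained, R² = f(1−f) × gain² / (25 + f(1−f) × gain²). The sample-size equivalent of adjustment is about 1/(1−R²).

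- R² = 0.10 gives 1.11, and R² = 0.20 gives 1.25.
- A 5-point gain with f from 20% to 50% gives R² from 4/29 = 0.14 to 6.25/31.25 = 0.20.
- A 2-point gain with f = 30% gives R² = 0.84/25.84 = 0.03, worth almost nothing.
- An 8-point gain with f = 50% gives R² = 16/41 = 0.39. Simulation of that case at 20 per arm lowered the SE from 2.02 to 1.59.

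**6. Average behaviour.** In simulations with no program effect and both arms assessed at the same week, the unadjusted analysis had a mean difference of about 0 and a type I error of about 0.04 to 0.06. Adjustment left both essentially unchanged and lowered the SE.

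**The case against.** The strongest reply is that randomisation already deals with this. It balances time since stroke in expectation, and the 5% error rate already allows for chance imbalance in any prognostic factor. That is correct, and step 6 agrees. A reader might infer from the open entry window that natural recovery will be mistaken for a program effect. The documents do not support that inference from the omitted covariate, because allocation is random. What remains is lost precision and the absence of any correction for the one allocation the trial will actually have.

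A second reply is that the magnitudes are all assumed and modest: an imbalance of 20 points is an unfavourable draw (the average absolute imbalance at 20 per arm and 30% early is about 11 points), and the resulting shift is under one standard error. This also stands, and it makes precision the firmer argument, since that loss does not depend on an imbalance occurring.

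Third, the documents do not say that time since stroke is among the characteristics tested, or that an exact date is recorded. Because recurrent stroke is admitted, the event that starts the clock is undefined. This is fair and is taken into the fix. Broad entry itself is a legitimate choice and is not criticised here.

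Finally, natural recovery can differ systematically between the arms by another route. "The condensed group will receive 4 sessions per week, for 6 weeks, the distributed group 2 sessions per week, for 12 weeks", and "The outcome will be measured at pre-treatment, mid-treatment" and at "post-treatment, and 6-week follow-up". If mid-treatment is halfway and follow-up is counted from the end of treatment, assessments fall at about weeks 3, 6 and 12 in one arm and weeks 6, 12 and 18 in the other. That is a separate problem. In simulations with an assumed 30% or 50% early patients gaining 2 or 4 points per 6 weeks, the spurious post-treatment difference was about 0.6 to 2.0 points in favour of the distributed arm, with or without the covariate.

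**Conclusion.** The point holds as one of efficiency and of uncorrected chance imbalance. It is not a finding of bias. The facts are plain in the documents: no upper limit on time since stroke, no stratification factor, no covariate, and baseline tests without consequence. The size is unknown. It rests on an assumed arm size, share of early patients, extra recovery and residual SD, and it ranges from negligible, if time since stroke is weakly prognostic, to the equivalent of 11% to 25% more participants at an assumed R² of 10% to 20%. The change is worth making because it is cheap and because prespecification is the only way to keep it from being chosen after an imbalance has been seen.

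**What to change.** In Data Analysis, prespecify time since the qualifying stroke, on the log scale because it is likely to be skewed, as a covariate with its interaction with visit in the between-program model for each outcome to which that model is applied. The interaction is needed: with complete data, a covariate entered only as a main effect shifts all visits equally and does not alter the group-by-time comparison. State that the covariate is kept whatever the baseline tests show, and that baseline significance tests will not be used to decide on adjustment. Define which event starts the clock in recurrent stroke, and record its date; screening must already establish that at least 3 months have passed.

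Stratified allocation by time since stroke is optional if enrolment is still open. Any cut-point would be a choice that the documents do not inform.

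The cost is a few model degrees of freedom (at an assumed 20 per arm, a two-group comparison has 40 − 2 = 38) and the recording of one date. There is little gain if the covariate is weakly prognostic. The different elapsed weeks of assessment in the two arms need their own remedy.

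### The aim is to compare the two programmes immediately and later, but no planned comparison gives the between-arm difference at post-treatment or at 6-week follow-up

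*Combined protocol and SAP*

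**What the plan says.** The opening section sets the aim as comparing the condensed with the distributed RT programme after BoNT-A injection, both immediately and in the longer term. It treats the combined treatment as established ("injection combined with robot-assisted training is recommended to enhance functional recovery for patients with spastic hemiplegic stroke") and gives RT frequency as the open question.

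Under Methods, participants are "randomly assigned to either condensed or distributed RT groups post BoNT-A injection". On content: "Each training session included 40 minutes RT, followed by 40-minute functional training". On schedule: "The condensed group will receive 4 sessions per week, for 6 weeks, the distributed group 2 sessions per week, for 12 weeks". Outcomes are taken at four visits, named by stage of treatment: pre-treatment, mid-treatment, post-treatment and a 6-week follow-up. Seven measures are listed and none is named as primary.

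Data Analysis puts three mixed-ANOVA tests under one purpose clause. The first is the time effect: "To examine the therapeutic effects of the RT, we use mixed ANOVA to test the differences within groups across 4 measurement time points". The other two are given as: "to test the differences between groups (condensed intervention group and distributed intervention group) and to test interaction effect between time and group". The only follow-up comparisons named are these: "Pairwise comparison with Bonferroni adjustments is used to examine the differences between measurement time points".

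**The concern.** The aim asks two specific questions: do the arms differ at the end of treatment, and do they differ later? None of the planned tests answers either one directly. The group effect has no visit attached. The interaction is an overall test. The pairwise comparisons are between visits, not between arms. A significant interaction would leave open whether the arms differ immediately, later or only at mid-treatment, and by how much. With seven measures and four visits, a contrast that is not named in advance can be chosen after the data are seen.

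A secondary point is wording. The time effect is listed among tests of the effects of RT, yet no arm or period without RT is planned. A significant time effect could then be read as showing that RT works.

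**Working it through.** The documents give no sample size, SD, effect size or planned power, so there is no figure to reproduce.

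**Treatment content (from Methods).** Condensed: 4 × 6 = 24 sessions. Distributed: 2 × 12 = 24 sessions. Each arm is therefore planned to have 24 × 40 min = 960 min = 16 h of RT, and the same amount of functional training. The two components always come one to one, so no sample size can separate them. Change over time may also include BoNT-A, recovery (entry is from 3 months after stroke, with no upper limit), repeat testing, and regression to the mean where entry requires a minimum Ashworth score. The documents do not allow the size of any of these to be judged.

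**Group effect.** It compares arm means over all four visits. For an arm difference d:
- at post-treatment and follow-up: (0 + 0 + d + d)/4 = d/2
- at post-treatment only: (0 + 0 + d + 0)/4 = d/4

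**Interaction.** Take n per arm, SD 1 and equal correlation rho. The noncentrality is n × Σ(d_t − d̄)² / (2(1 − rho)). For d at any one visit after baseline, Σ(d_t − d̄)² = d²(1 − 1/4) = 0.75d². The value is the same for mid-treatment, post-treatment or follow-up, so the 3-df test responds identically to all three and cannot tell them apart.

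**Power for d = 0.5 SD at post-treatment only.** All inputs are assumed. The contrast is a two-sample t test on change from pre-treatment, with variance of change 2(1 − rho). The group effect uses a mean difference of d/4 and variance (1 + 3rho)/4 for each participant's four-visit mean.

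| rho | n per arm | Interaction, 0.05 | Contrast, 0.05 | Contrast, 0.025 | Group effect, 0.05 |
|---|---|---|---|---|---|
| 0.5 | 15 | 0.248 | 0.262 | 0.176 | 0.070 |
| 0.5 | 20 | 0.327 | 0.338 | 0.238 | 0.078 |
| 0.5 | 30 | 0.480 | 0.478 | 0.364 | 0.092 |
| 0.7 | 15 | 0.398 | 0.400 | 0.290 | 0.066 |
| 0.7 | 20 | 0.521 | 0.512 | 0.395 | 0.072 |
| 0.7 | 30 | 0.720 | 0.691 | 0.581 | 0.084 |

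The interaction and a contrast at 0.05 have similar power, and the group effect has little. At 0.025 the contrast has less power than the interaction in every row.

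**Multiplicity of the added contrasts.** Two contrasts × 7 measures = 14. If they were independent and each tested at 0.025, the chance of at least one false positive would be 1 − 0.975^14 = 0.298, about 30%.

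**The case against.** The strongest reply is that the randomised comparison is already tested. The group-by-time interaction is valid, it is planned, and under the assumptions above it has about the same power as a single contrast at 0.05. Following a significant interaction with comparisons at each visit is routine, and a short plan need not spell it out. The first part of this stands in full. The second part stands less well, because the plan does name its follow-up comparisons and they are only between time points.

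On wording, the clause about RT introduces all three tests, not the time effect alone, and may be shorthand for the two RT programmes. The background treats the combined treatment as the premise, and the aim includes determining effects as well as comparing them, which within-arm change can serve descriptively. All of this is fair, and it makes the wording a secondary matter.

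A reader might infer that the plan has no between-arm test, or that it intends to claim RT efficacy from change over time. The documents support neither. Two between-arm tests are planned, and nowhere does the text say that a significant time effect will be presented as evidence for RT.

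**Conclusion.** This is a cheap improvement, not a fault that invalidates the trial. What holds is that no planned comparison gives the between-arm difference at either of the visits the aim calls for. The d/2 and d/4 dilution of the group effect, and the inability of the interaction to identify the visit, follow from the design by arithmetic. The power figures are illustrations that rest on assumed n, SD, correlation and effect profile. The gain from naming contrasts is an interpretable, prespecified answer with an effect size. It is not a gain in power.

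The secondary point holds in a limited form: whatever the clause was meant to say, change over time here is change under BoNT-A, RT and functional training together and cannot be credited to RT. A significant time test would not be a false positive if both arms really change; the problem would lie only in attributing that change to RT. A reader might go further and conclude that the randomised comparison of programmes is compromised, but nothing in the documents supports that.

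**What to change.** 1. State the purpose as comparing the condensed with the distributed programme, and keep the group-by-time interaction as the overall between-arm test.
2. For each measure, add two prespecified between-arm contrasts in change from pre-treatment: to post-treatment (immediate) and to 6-week follow-up (longer-term). State that they are reported whatever the interaction shows.
3. Give each contrast an estimate and an interval that matches its test level: a 97.5% CI if each is tested at 0.025 by Bonferroni, or a 95% CI if unadjusted and labelled as such.
4. Say that this adjustment covers the two visits, not the seven measures. Either name one measure for the confirmatory contrasts, or label the contrasts on the other measures exploratory.
5. Report the time effect and the pairwise time comparisons as within-arm change under BoNT-A, RT and functional training, with no efficacy claim for RT. State whether the pairs are pooled (4 × 3/2 = 6 per measure) or run by arm (12).
6. State the time scale of the visits. The documents give no calendar weeks. If visits follow each arm's own course and follow-up is counted from the end of treatment, post-treatment falls at about week 6 or 12 and follow-up at about week 12 or 18. The contrasts should then be described as comparing whole programmes, frequency and length together.

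The cost is SAP text and two contrasts per measure (14 in all), with no new data. Under the assumed inputs, adjusting for two visits lowers the power of a contrast from 26% to 69% at 0.05 to 18% to 58% at 0.025. That is below the interaction's 25% to 72%, which is one reason to retain the interaction.

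### The four-visit mixed ANOVA, run in its usual classical form, deletes everyone who misses one visit; the plan states no procedure or missing-data rule, and a REML mixed model in the same software would keep their scores

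*Combined protocol and SAP*

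**What the plan says.** The opening aims are to "determine and compare the immediate and longer-term effects between condensed and distributed programs of RT following BoNT-A injection". In Methods, "The condensed group will receive 4 sessions per week, for 6 weeks, the distributed group 2 sessions per week, for 12 weeks", and outcomes are taken at pre-treatment, mid-treatment, "post-treatment, and 6-week follow-up". The impairment outcomes are listed thus: "Body function and structures outcome measures include Fugl-Meyer Assessment, Modified Ashworth Scale, actigraphy". Three scales of arm use and everyday performance, and Goal Attainment Scaling, are added.

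For the treatment comparison, Data Analysis states "we use mixed ANOVA to test the differences within groups across 4 measurement time points (time effect", then tests group differences and goes on "to test interaction effect between time and group". Bonferroni-adjusted pairwise comparisons between visits follow, all in SPSS 25 at the 0.05 level.

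The document does not name the SPSS procedure, the estimation method, a covariance structure, an analysis population or the handling of missed visits. It gives no sample size or expected dropout.

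**The concern.** A mixed ANOVA with one within-subject factor, one between-subject factor and their interaction most naturally means the classical split-plot analysis. In general statistical practice (this is not stated in the document) that analysis needs a complete row of four scores per participant and discards incomplete rows. SPSS also offers a linear mixed model procedure, MIXED, which uses whatever scores were observed. The plan does not say which is meant.

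Under the classical reading, loss at the last visit damages the earlier comparison too. Someone assessed at pre-, mid- and post-treatment who misses the follow-up contributes nothing, even to the immediate effect. The trial compares two active programs of equal session count (4 × 6 = 2 × 12 = 24), so the difference may be small and precision matters.

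**Working it through.** The plan has no figure to reproduce. From the document come the four visits (three post-baseline), two arms and the schedules. Assumed are a miss rate *d* per post-baseline visit of 5% or 10%, baseline always observed, and between-visit correlation of 0.5, 0.7 or 0.85, compound symmetric or autoregressive. Monotone means that a participant who misses a visit never returns.

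**1. Participants deleted**, 1 − (1 − d)³, under either pattern:
- d = 5%: 1 − 0.95³ = 0.143
- d = 10%: 1 − 0.90³ = 0.271

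**2. Deleted although the post-treatment score was observed:**
- Independent misses, (1 − d)[1 − (1 − d)²]: 0.95 × (1 − 0.95²) = 0.093; 0.90 × (1 − 0.90²) = 0.171
- Monotone, (1 − d)²d: 0.95² × 0.05 = 0.045; 0.90² × 0.10 = 0.081

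**3. Precision of the arm difference in change.** Let Σ be the 4 × 4 covariance and *c* the contrast (−1, 0, 1, 0) for post-treatment or (−1, 0, 0, 1) for follow-up. Per participant, V(completers) = c′Σc / (1 − d)³. V(likelihood) = c′I⁻¹c, where I sums, over missingness patterns, the pattern probability times the inverse of Σ restricted to the observed visits. The covariance is treated as known.

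Example: correlation 0.7, compound symmetry, d = 10%. Information relative to complete data is 0.729 for completers. For the likelihood model it is 0.932 (independent), giving a ratio of 0.932 / 0.729 = 1.278. Under monotone dropout it is 0.846 at post-treatment (ratio about 1.16) and 0.787 at follow-up (ratio about 1.08).

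Variance ratio, completers to likelihood, over all assumed correlations:

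| Pattern | d = 5% | d = 10% |
|---|---|---|
| Independent | 1.127–1.148 | 1.276–1.324 |
| Monotone, post-treatment | 1.071–1.100 | 1.150–1.213 |
| Monotone, follow-up | 1.035–1.076 | 1.069–1.155 |

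**4. As power.** Suppose full data gave 80%. Power is Φ(2.802√info − 1.960). With the example's values at post-treatment, completers have Φ(2.802√0.729 − 1.960) = 67%. The likelihood model has 77% (info 0.932, independent) or 73% (info 0.846, monotone).

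**5. Small samples, covariance estimated.** In simulations with 15, 20 or 30 per arm, correlation 0.7 and d = 10% (2,500 runs each), the completer variance was 27–32% larger (independent) or 5–17% larger (monotone). The unstructured REML model always converged. Type I error at nominal 0.05 was 0.046–0.063 with Satterthwaite, 0.054–0.075 with a normal reference and 0.042–0.060 for the completer t test.

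**6. Bias, one scenario with equal completion.** Assume no true difference, compound symmetry with correlation 0.7, and 16.7% dropout after mid-treatment in each arm. In one arm dropout follows poor change to mid-treatment; in the other it is random. With unit variances, the covariance of change-to-post with change-to-mid is 0.7 − 0.7 − 0.7 + 1 = 0.3, so completers' change is shifted. The covariance of the post-treatment level with change-to-mid is 0.7 − 0.7 = 0, so the level is not. By simulation, the completer bias in change is 0.056 SD at a log-odds slope of 1 per SD of change and 0.099 SD at a slope of 3, while the level bias is near zero. With a slope of 1.5 and 200,000 per arm, completers gave 0.076 SD and maximum likelihood 0.002 SD.

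**The case against.** The harm is doubly conditional: it needs the classical procedure and it needs missed visits, and the document establishes neither. Candidates are excluded for "medical conditions that would prevent adherence to the rehabilitation protocol", which may keep dropout low. All of this stands. What is certain is only that the procedure and missing-data rule are unstated.

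The count of deleted participants also overstates the information lost. Withdrawals from a therapy course are plausibly mostly monotone, and there the penalty is modest. That stands too, so the monotone figures should be read alongside the larger ones.

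A reader might infer that 12 weeks of therapy against 6 must bias the completer analysis against one arm. The document does not support this. Both arms have 24 sessions; if dropout per session and follow-up loss are equal and depend on scores in the same way, the bias is zero. Illustrative scenarios with unequal completion gave shifts of either sign.

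The opposite inference, that bias is negligible or bounded by some small value, is not supported either. Step 6 gives up to about 0.10 SD with equal completion, and other patterns were not exhausted.

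Nor does a likelihood model cure informative dropout. When missingness depended on the unseen score (MNAR), with equal weekly dropout of 1% or 2%, its bias in change reached 0.06 SD against 0.03 SD for completers.

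**Conclusion.** The concern holds as a conditional loss of data and precision. If the ANOVA is classical and 5% or 10% miss each post-baseline visit, 14% or 27% of participants are deleted. The variance of the arm difference in change is then about 4–10% or 7–21% larger than necessary under monotone dropout, and 13–15% or 28–32% larger if misses are independent (correlation 0.5–0.85). Every one of these inputs is assumed.

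Bias is secondary. It can arise when dropout depends on earlier scores differently by arm; no general size, sign or upper bound should be claimed. A likelihood model removes it under missing at random (MAR) but not under MNAR.

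The plan does not say that participants will be deleted, and with complete follow-up nothing is lost. The change is still worth making because it is cheap and settles who is analysed.

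**What to change.** For the continuous or approximately continuous outcomes (for example Fugl-Meyer, Wolf Motor Function Test, Motor Activity Log, Canadian Occupational Performance Measure, actigraphy), replace the mixed ANOVA with a REML linear mixed model in SPSS MIXED, or state that this was intended. The Modified Ashworth Scale and Goal Attainment Scaling are outside this point. The SAP should specify:

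- all observed visits, including pre-treatment, of every randomised participant in the assigned arm;
- fixed effects for group, visit and group × visit;
- an unstructured covariance, with a stated simpler fallback (such as heterogeneous compound symmetry) if it does not converge;
- Satterthwaite degrees of freedom;
- arm differences in change from pre-treatment to post-treatment and to 6-week follow-up, matching the two aims;
- the MAR assumption, and the number observed by arm and visit.

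An MNAR sensitivity analysis is optional. It would need a key outcome named in advance, which the plan does not yet have, and it is real extra work.

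The cost of the main change is SAP wording, with the same data and software. The downside is a covariance with 4 × 5 / 2 = 10 parameters in a trial of unstated size, which is why the fallback and degrees-of-freedom method should be fixed in advance.

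### The pre-treatment score is one of four outcome visits in the mixed ANOVA and is adjusted for nowhere, so both planned between-group tests lose precision and carry chance baseline differences

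*Combined protocol and SAP*

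**What the plan says.** The Methods section gives the visit schedule: "The outcome will be measured at pre-treatment, mid-treatment", followed by post-treatment and a 6-week follow-up. That makes four visits, and the first precedes training.

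The Data Analysis section puts all four into one model: "we use mixed ANOVA to test the differences within groups across 4 measurement time points (time effect"). The same sentence names two tests that involve the programs:

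- a group effect, "to test the differences between groups (condensed intervention group and distributed intervention group");
- an interaction, "to test interaction effect between time and group".

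It does not say which of the two decides between the programs. The follow-up tests are within the time factor: "Pairwise comparison with Bonferroni adjustments is used to examine the differences between measurement time points". No between-group contrast at a named visit is given.

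The only other use of baseline is a significance test: "we use the chi-square test and independent-sample t tests to compare participants' baseline characteristics between groups". Nothing follows from its result. No covariate or ANCOVA appears anywhere in the document.

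**The concern.** The trial aims to compare two training schedules, both immediately and in the longer term. For that purpose the pre-treatment score is information about each patient and cannot itself be an effect of the schedule. Making it a level of the time factor affects the two tests differently.

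- **Interaction.** It asks whether the pattern over the four visits differs between arms. When the effect is the same at all later visits, this amounts to comparing changes from baseline. A change score fixes the slope on baseline at 1, whereas ANCOVA estimates it. The test also spreads the signal over (2 − 1) × (4 − 1) = 3 numerator degrees of freedom.
- **Group main effect.** It averages all four visits, one of which cannot show an effect, and leaves the between-patient variance in the error term.

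At stake are precision that the trial could have from data it already collects, and the reading of the result if the arms happen to differ at entry. The entry range leaves room for that: "initial motor part of UE of FMA score ranging from 12 to 56".

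**Working it through.** The documents give no sample size, power, effect size, SD or correlation, so there is no stated figure to reproduce. What follows is an illustration.

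**Inputs from the documents.** Two randomised groups; four visits including pre-treatment; testing "at the $\alpha = .05$ level of significance"; Fugl-Meyer 12 to 56 at entry.

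**Assumptions.** 1:1 allocation, two-sided tests, unit SD at each visit, the same correlation r between any two visits, an effect δ that is equal at the three later visits, complete data, n per arm.

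**Variance factors** (variance of the estimated difference = factor × 2/n):

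- One visit: change 2(1 − r); ANCOVA 1 − r². Ratio (1 + r)/2 = 0.75, 0.85, 0.95 at r = 0.5, 0.7, 0.9.
- Mean of three later visits: change (4/3)(1 − r); ANCOVA (1 + 2r)/3 − r². Ratio (1 + 3r)/4 = 0.625, 0.775, 0.925.
- Group main effect: variance (1 + 3r)/4 for an effect of (0 + δ + δ + δ)/4 = 0.75δ. Rescaled to δ, the factor is [(1 + 3r)/4]/0.5625 = 4(1 + 3r)/9.

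**Small samples.** Estimating the slope multiplies the ANCOVA variance by about 1 + 1/(2n − 4): 1.038 at n = 15 and 1.018 at n = 30. At r = 0.9 the single-visit ratio becomes 0.95 × 1.038 = 0.99 with 15 per arm, and 0.97 with 30.

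**Power with n = 20 and δ = 0.5 SD.** The noncentrality is (n/2)δ²/factor = 2.5/factor. At r = 0.7:

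| Test | Factor | Noncentrality | df | Power |
|---|---|---|---|---|
| Group main effect, four visits | 1.378 | 1.81 | 1, 38 | 26% |
| Group-by-time interaction | 0.400 | 6.25 | 3, 114 | 52% |
| Change, mean of later visits | 0.400 | 6.25 | 1, 38 | 68% |
| ANCOVA, mean of later visits | 0.310 | 8.06 | 1, 37 | 79% |

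Allowing for the estimated slope lowers the last figure to about 78%. In the same order, power is 31%, 33%, 47% and 66% at r = 0.5, and 23%, 96%, 99% and 99% at r = 0.9.

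The step from 52% to 68% comes from using one degree of freedom instead of three. The step from 68% to 79% comes from baseline adjustment. At a single visit with r = 0.7, power is 51% for a change score and 58% for ANCOVA (noncentrality 2.5/0.60 = 4.17 and 2.5/0.51 = 4.90).

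**Carry-over of a chance baseline difference d.** Later visits are expected to differ by rd.

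- Change: rd − d = −(1 − r)d, which is −0.30d at r = 0.7.
- Group main effect: (d + 3rd)/4 = (1 + 3r)d/4, which is +0.775d at r = 0.7.
- ANCOVA: about 0.

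A simulation of 40,000 trials with 20 per arm and r = 0.7 gave −0.298, +0.776 and +0.003.

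**On the Fugl-Meyer scale.** If scores were spread evenly over 12 to 56, the SD would be 44/√12 = 12.7. With 20 per arm, a 1-SD chance difference is 12.7 × √(2/20) = 4.0 points. At r = 0.7 it moves the change comparison by −0.30 × 4.0 = −1.2 points and the main effect by +0.775 × 4.0 = +3.1 points.

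**The case against.** The case for leaving the plan alone has four parts.

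1. **Validity.** The arms are randomised, so both planned tests are unbiased on average, and having baseline as a response does not in itself inflate the type I error. This stands. A reader might infer from the carry-over figures that the result would be biased. The documents do not support that: the carry-over is conditional on the imbalance that happens to occur, and it averages to zero over randomisations.

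2. **The gain may be small.** At r = 0.9 the variance saving against a change score is 5% at one visit, and only 1% to 3% once the slope is estimated with 15 to 30 per arm. Other things equal, a wide entry range raises r. This stands against any claim of a large gain over a change score. It does not rescue the group main effect, which gets worse as r rises.

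3. **The plan is not simply a change-score analysis.** A reader might conclude that the whole comparison between programs is one of change scores. That describes only the interaction; the plan also names a group effect, which behaves differently and carries imbalance the other way. Nor do the variance ratios measure what this plan loses, because they concern 1-df contrasts that the plan does not specify.

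4. **A small true difference cannot be presumed.** Both arms receive 24 sessions (4 × 6 and 2 × 12), but the document calls the best frequency unknown. That is right, and the point does not need the premise: the efficiency argument applies whatever the size of the effect.

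**Conclusion.** The concern holds as a matter of efficiency and conditional imbalance. The pre-treatment score is one of the four response visits, nothing adjusts for it, and both planned between-group tests lose precision against a baseline-adjusted model and pass on chance baseline differences with opposite signs. The analysis is not invalid.

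That conclusion rests on the wording of the plan. Its size does not: n, SD and r are assumed throughout, as are equal correlations and a constant later effect. Under those assumptions the loss against a change score is material at r of 0.5 to 0.7 and slight near 0.9, while the dilution of the group main effect to 75% is the same at any r. The 79% applies to the mean of the later visits and should not be read as the power at any one visit.

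The change should be made because it costs almost nothing and also settles which contrasts answer the trial's question.

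**What to change.** For each continuous outcome with a true pre-treatment score (Fugl-Meyer, Wolf Motor Function Test, Motor Activity Log, Canadian Occupational Performance Measure, actigraphy), replace the between-program part of the Data Analysis paragraph with the following:

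- Response visits: mid-treatment, post-treatment and 6-week follow-up.
- Model: a repeated-measures model (SPSS MIXED) with group, visit, group-by-visit, the pre-treatment score of that outcome, and pre-treatment score by visit.
- Between-program results: the adjusted differences at post-treatment (immediate) and at 6-week follow-up (longer term), with confidence intervals. These take the place of the four-visit group main effect and interaction as the between-program tests.

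The within-group comparisons across visits, with their Bonferroni adjustment, can stay as planned. The Modified Ashworth Scale is ordinal, and Goal Attainment Scaling may lack a baseline score in the same sense; each needs its own stated analysis.

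The cost is a change of wording, made before outcome data are seen by group. The baseline is already collected, SPSS is already the named software, and the covariate terms use one to three degrees of freedom.
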